5.2.1.2. Generalized Linear Mixed Model and Tipping Point – Analyses 2 and 2a

As a supplementary analysis, the primary endpoint for the overall study and for the FDA/PMDA will also be analyzed utilizing a generalized linear mixed model (GLMM) for longitudinal binary data of response based on $SALT \leq 20$ over time up to Week 24. This binary outcome will be modeled using a logistic-normal distribution. Fixed factors in this model are treatment (6 levels), visit (5 levels) and treatment-by-visit interaction. Visit will be modeled as a categorical covariate. A subject-specific random intercept will be used to model the correlation within a subject over time. Due to the expected negligible placebo response, a Bayesian estimation will be carried out in which diffusive priors will be used and the placebo response probability will be bounded away from 0 to avoid the potential convergence issues. From this model, one can derive the estimates of the marginal probability of response for each treatment group at each visit as well as inferential comparisons (the proportional difference between active and placebo groups, CIs and p-values) between treatment groups after the random effect is integrated out from the posterior samples. Given that this random intercept model specifies the full joint distribution for the outcome, the inference for the marginal proportions will be valid in the presence of missing data when the missing mechanism is missing at random (MAR). This inference will be with respect to the difference in treatments assuming all subjects maintained their randomized therapy. This analysis will be referred to as Analysis 2.

A tipping point analysis will be conducted under the assumption of missing not at random (MNAR). The imputations will be implemented under the framework of the same logit normal GLMM as above. Imputation of missing SALT response is performed only at Week 24 based on the predictive distribution of the GLMM. Under MNAR assumption, a fixed MNAR quantity (favorable or unfavorable), delta, will be applied to the probability of response at Week 24 for subjects with missing SALT response in the PF 06651600 dose groups and placebo group independently to assess when the conclusion might change (ie, tipping). Imputations will be repeated to obtain completed datasets. The Rubin's rules^{4,6} will be used to combine the results of multiple imputed samples for inference. This analysis will be referred to as Analysis 2a.

A scenario included in the tipping point analysis framework is an analysis under MAR, if there is no fixed quantity applied to the probability of response for each subject in the PF-06651600 dose groups or the placebo group, ie, when delta is zero.

Detailed descriptions of the tipping point analyses are provided in [Section 9.6](#).

5.2.1.3. Generalized Linear Mixed Model and Tipping Point – Analyses 4 and 4a

The primary analysis of the primary endpoint for the EMA and competent authorities in the VHP countries will be based on a MAR assumption and use multiple imputation methods similar to those described in [Section 5.2.1.2](#). In this analysis, while subjects with missing SALT scores due to COVID-19 will be assumed to be MAR, subjects with missing SALT scores due to other reasons will be treated as non-responders. This analysis will be referred to as Analysis 4.

A tipping point analysis will be conducted similar to that described in [Section 5.2.1.2](#). While the analysis for the study and for the FDA/PMDA will treat missing as MNAR regardless of the reason for missingness, the analysis for the EMA will treat missing due to COVID-19 as MNAR but missing due to other reasons will be considered as non-responders. This analysis will be referred to as Analysis 4a.

The key secondary endpoint, PGI-C response at Week 24, will also be analyzed using this approach.

5.2.1.4. Descriptive Analysis of Binary Endpoints

All secondary binary endpoints in the placebo-controlled phase will be analyzed in the same way as Analysis 1 in [Section 5.2.1.1](#).

Exploratory binary endpoints will be summarized using descriptive statistics unless specified otherwise.

Summaries of data from baseline to Week 48 (over the entire study) will include number of responders, percent, standard error, 95% CI based on normal approximation. These summaries will be based on observed cases, and data will be presented by 7 treatment sequences (ie, without combining the placebo groups F and G, [Figure 1](#)).

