### **9.2.3. Analysis of Secondary Endpoints**

For all regions, analyses of secondary endpoints that are not  $\alpha$  controlled will use the approach outlined below.

Secondary endpoints that are binary variables will be analyzed using the same approach as Analysis 1 in [Table 6](#).

For continuous endpoints, a mixed-effects model with repeated measures (MMRM) will be used. This model will include the factors (fixed effects) for treatment group, visit, treatment-by-visit interaction, and relevant baseline value when modeling change from baseline. Within the framework of MMRM, the treatment difference will be tested at each time point.

All secondary endpoints will be evaluated at the 5% level of significance, without adjustment for multiple comparisons.

Details on the analysis of individual secondary endpoints will be provided in the SAP.

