
a. The VHP countries participating in this study are Czech Republic, Germany, Hungary, Poland, and Spain.
 
b. For the EMA and competent authorities in the VHP countries, when SALT ≤10 is utilized for the primary endpoint, exposure response will be analyzed utilizing SALT ≤10 in a separate analysis.
	

[figure not shown]

- c. For the EMA and competent authorities in the VHP countries, when SALT ≤ 10 is utilized for the primary endpoint, SALT ≤ 20 at Week 24 will be analyzed as a secondary endpoint.
- d. When SALT ≤ 20 response at Week 24 is utilized as the primary endpoint, responses based on absolute SALT score ≤ 20 at Weeks 18, 12, 8 and 4 will be analyzed controlling for Type I error utilizing an appropriate testing procedure. When SALT ≤ 10 response at Week 24 is utilized as the primary endpoint, the response based on absolute SALT score ≤ 20 at Week 24 will be analyzed controlling for Type I error utilizing an appropriate testing procedure.
- e. When SALT ≤ 20 response at Week 24 is utilized as the primary endpoint, the response based on absolute SALT score ≤ 10 at Week 24 will be analyzed controlling for Type I error utilizing an appropriate testing procedure. When SALT ≤ 10 response at Week 24 is utilized as the primary endpoint, the responses based on absolute SALT score ≤ 10 at Weeks 18, 12, 8 and 4 will be analyzed controlling for Type I error utilizing an appropriate testing procedure.
- f. For the EMA and competent authorities in the VHP countries, the evaluation of the effect of PF-06651600 on patient centered outcomes (as measured by PGI-C response at Week 24) is a key secondary objective. The PGI-C response at Week 24 will be analyzed as a key secondary endpoint utilizing an appropriate testing procedure to control overall Type I error.
- g. For the EMA and competent authorities in the VHP countries, endpoints utilizing the HADS will be analyzed as secondary endpoints.

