	
 • Change from baseline in SALT scores at Weeks 4, 8, 12, 18, 24, 28, 34, 40, and 48. • Response based on at least a 2-grade improvement or a score of 3 in EBA score at Weeks 4, 8, 12, 18, 24, 28, 34, 40, and 48. • Response based on at least a 2-grade improvement or a score of 3 in ELA score at Weeks 4, 8, 12, 18, 24, 28, 34, 40, and 48. • PGI-C response defined as a PGI-C score of “moderately improved” or “greatly improved” at Weeks 4, 8, 12, 18, 24, 34, 40, and 48. • Change from baseline in AAPPO scales at Weeks 4, 8, 12, 18, 24, 34, 40, and 48. - - - - 	
 • Change from baseline in SALT scores at Weeks 4, 8, 12, 18, 24, 28, 34, 40, and 48. • Response based on at least a 2-grade improvement or a score of 3 in EBA score at Weeks 4, 8, 12, 18, 24, 28, 34, 40, and 48. • Response based on at least a 2-grade improvement or a score of 3 in ELA score at Weeks 4, 8, 12, 18, 24, 28, 34, 40, and 48. • PGI-C response defined as a PGI-C score of “moderately improved” or “greatly improved” at Weeks 4, 8, 12, 18, 24, 34, 40, and 48. • Change from baseline in AAPPO scales at Weeks 4, 8, 12, 18, 24, 34, 40, and 48. • Change from baseline in the depression subscale score of the HADS at Weeks 4, 8, 12, 24, and 48. • Change from baseline in the anxiety subscale score of the HADS at Weeks 4, 8, 12, 24, and 48. • Improvement on HADS among subjects with a baseline subscale score indicative of depression who achieved a “normal” subscale score indicative of an absence of depression at Weeks 4, 8, 12, 24, and 48. • Improvement on HADS among subjects with a baseline subscale score indicative of anxiety who achieved a “normal” subscale score indicative of an absence of anxiety at Weeks 4, 8, 12, 24, and 48.

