- For the EMA and competent authorities in the VHP countries this endpoint will be analyzed as a secondary endpoint.
- Among adults, a score of 0-7 is considered normal, a score of >7 is indicative of depression. Among adolescents (at baseline age), a score of 0-6 is considered normal, a score of >6 is indicative of depression;^{2,3}
- Improvement on HADS among subjects with a baseline subscale score indicative of anxiety who achieved a “normal” subscale score indicative of an absence of anxiety at Weeks 4, 8, 12, 24, and 48.
 - For the EMA and competent authorities in the VHP countries this endpoint will be analyzed as a secondary endpoint.
 - Among adults, a score of 0-7 is considered normal, a score of >7 is indicative of anxiety. Among adolescents (at baseline age), a score of 0-8 is considered normal, a score of >8 is indicative of anxiety.^{2,3}
- Change from baseline in 36-Item Short Form Health Survey version 2 Acute (SF36v2 Acute) at Weeks 4, 8, 12, 24, and 48.
 - 8 domain scales: physical function (PF), bodily pain (BP), role physical (RP), role emotional (RE), Vitality (VT), general health (GH), social function (SF), and mental health (MH).
 - 2 summary scales: Mental Component Summary Score (MCS) and Physical Component Summary Score (PCS).
- Change from baseline in Clinician Global Impression – Alopecia Areata (CGI-AA) at Weeks 4, 8, 12, 18, 24, 28, 34, 40, and 48.
 - CGI-AA scored as 0=‘None (no hair loss)’, 1=‘Minimal hair loss’, 2-4= ‘Moderate-very severe or complete hair loss’.
 - Improvement among participants with a baseline score 2-4 indicating Moderate-very severe or complete hair loss who achieved a score of 0=‘None (no hair loss)’ or 1=‘Minimal hair loss’.
- Change from baseline in fingernails affected by AA at Weeks 12, 24, 34, 40, and 48.
- Change from baseline in interferon gamma-induced protein 10 (IP-10) at Weeks 4, 8, 12, and 24.
- Change from baseline in percent and absolute lymphocyte subsets (T-cell, B-cell, and natural killer [NK] cells) at Weeks 4, 12, 24, and 48.
- Change from baseline in immunoglobulins (IgA, IgG, IgM) at Weeks 24 and 48.

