6.2. Secondary Endpoints

The analysis of binary secondary endpoints in the placebo-controlled phase will use the same approach in Analysis 1 ([Section 5.2.1.1](#)).

6.2.1. Exposure Response for Response Based on SALT Score ≤ 20 at Week 24

- Response based on SALT Score ≤ 20 at Week 24.
- Population: FAS.
- Statistical Method: Bayesian three-parameter E_{\max} model with the log odds (logit) of the probability of response based on SALT score ≤ 20 at Week 24 ([Section 5.2.2](#)).
- Missing Data: Exclude missing due to COVID-19, consider missing due to other as non-responders.

6.2.2. Exposure Response for Response Based on SALT Score ≤ 10 at Week 24

- Response based on SALT Score ≤ 10 at Week 24.
- Population: FAS.
- Statistical Method: Bayesian three-parameter E_{\max} model with the log odds (logit) of the probability of response based on SALT score ≤ 10 at Week 24 ([Section 5.2.2](#)).
- Missing Data: Exclude missing due to COVID-19, consider missing due to other as non-responders.

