6.3.10. Improvement on Depression Subscale of HADS

- Improvement on HADS among subjects with a baseline subscale score indicative of depression who achieved a “normal” subscale score indicative of an absence of depression at Weeks 4, 8, 12, 24, and 48.
- Population: Subjects from the FAS with a baseline subscale score indicative of depression (ie, depression subscale score >7 for adults, depression subscale score >6 for adolescents).
- Statistical Method: MN up to week 24. Descriptive method for entire duration.
- Missing Data: Observed Case.

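### HADS improvement is secondary for the EMA but is compared on observed cases, against the SAP's own rule for secondary binary endpoints; and the by-sequence responder intervals use a normal approximation that fails at low rates with about 60 subjects

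*SAP*

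**What the plan says.** **Status of HADS improvement.** For the overall study and FDA/PMDA, the depression and anxiety improvement endpoints are exploratory. For the EMA and VHP authorities, note g to SAP Table 2 says that "endpoints utilizing the HADS will be analyzed as secondary endpoints". SAP 3.2.1 repeats under each improvement endpoint: "For the EMA and competent authorities in the VHP countries this endpoint will be analyzed as a secondary endpoint". SAP Table 4 and Protocol Table 5 list both in the EMA column.

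**Rule for secondary binary endpoints.** SAP 5.2.1.4: "All secondary binary endpoints in the placebo-controlled phase will be analyzed in the same way as Analysis 1". SAP 6.2: "The analysis of binary secondary endpoints in the placebo-controlled phase will use the same approach in Analysis 1". Protocol 9.2.3 opens with "For all regions, analyses of secondary endpoints that are not" alpha-controlled, assigns the binary ones to Analysis 1, and has secondary endpoints evaluated at 5% without multiplicity adjustment. Analysis 1 (SAP 5.2.1.1) is the Miettinen-Nurminen (MN) method with COVID-19 missing excluded and other missing counted as non-response.

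**What is specified for HADS improvement.** SAP 6.3.10: "Statistical Method: MN up to week 24. Descriptive method for entire duration" and "Missing Data: Observed Case". SAP 6.3.11 does the same for anxiety.

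**Interval method.** For baseline to Week 48, SAP 5.2.1.4 asks for responder counts, percentages, standard errors and normal-approximation 95% intervals, on observed cases, for seven sequences with placebo sequences F and G kept apart.

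**The concern.** For the EMA, two parts of the SAP give different missing-data rules for the same comparison. On observed cases, a subject missing for a non-COVID reason drops out of the HADS comparison. In the other EMA secondary binary endpoints that subject is a failure. If missingness differs by arm, the choice can move the difference in either direction, so it should be settled before unblinding.

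On the intervals, the plan itself expects very low response in the small sequences. SAP 5.2.1.2 anticipates almost no placebo response, the sample size section assumes a placebo rate of at most 5%, and Protocol 1.6 describes 10 mg as probably minimally efficacious. The normal-approximation interval is least reliable there, and with no responders it has zero width.

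**Working it through.** **1. Sequence sizes.** 660 subjects at 2:2:2:2:1:1:1 gives 660/11 = 60 for the 10 mg, F and G sequences and 2 × 60 = 120 for each of the other four. This reproduces the stated 60 for 10 mg and 120 for the main groups (SAP 2.2.1).

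**2. Does any text release HADS from Analysis 1?** In SAP 5.2.1.4 the allowance for other specifications attaches only to exploratory endpoints; the sentence on secondary endpoints has none. SAP 5.3 leaves exploratory endpoints unimputed, which is the likely origin of the observed-case line. SAP 5.3.1 lists six approaches for binary endpoints, and observed case is not among them. The nearest comparator is AAPPO items 1-4 (SAP 6.2.10), also a patient-reported improvement endpoint among subjects abnormal at baseline and also analysed by MN. It carries the Analysis 1 missing-data rule.

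**3. Size of the HADS choice.** The documents give no HADS rates, missingness or subset size, so all inputs here are assumed. With observed rates p1 and p0 and non-COVID missing fractions d1 and d0, the Analysis 1 difference is p1(1 − d1) − p0(1 − d0). For 50% and 40% (observed-case difference 10 points):

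- Equal missingness of 5, 10, 15 or 20%: 9.5, 9.0, 8.5 or 8.0 points.
- Active 5%, placebo 15%: 47.5 − 34.0 = 13.5 points.
- Active 15%, placebo 5%: 42.5 − 38.0 = 4.5 points.

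For p-values, the MN score statistic at zero difference is z = (p1 − p0) / √[p̄(1 − p̄)(1/n1 + 1/n0) × N/(N − 1)], where p̄ is the pooled rate. Take 60% and 30%, with 36 per arm (an assumed 30% of 120 abnormal at baseline) and missingness 15/5%.

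- Observed cases: n = 30.6 and 34.2, p̄ = 0.442, z = 0.30/0.1245 = 2.41, p = 0.016.
- Analysis 1: n = 36 and 36, rates 51% and 28.5%, p̄ = 0.3975, z = 0.225/0.1162 = 1.94, p = 0.053.

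The same formula over other assumptions:

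| Per arm | Missing, active/placebo | Observed-case p | Analysis 1 p |
|---|---|---|---|
| 18 | 15/5% | 0.09 | 0.17 |
| 36 | 15/5% | 0.016 | 0.053 |
| 36 | 5/15% | 0.016 | 0.007 |
| 36 | 10/10% | 0.016 | 0.02 |
| 60 | 15/5% | 0.002 | 0.012 |

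**4. Coverage of the normal-approximation interval.** The interval is x/n ± 1.96√[(x/n)(1 − x/n)/n]. Exact coverage sums the binomial probabilities of every x whose interval contains the true rate. The range n = 48 to 60 assumes 0 to 20% missing.

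| True rate | Coverage, n = 60 | Range, n = 48-60 |
|---|---|---|
| 1% | 45% | 38-45% |
| 2% | 70% | 62-70% |
| 5% | 81% | 91-95% at n = 48-58, then about 80% |
| 10% | 94% | 86-94% |
| 20-40% | 92-95% | 91-96% |

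The drop at 5% arises because 1/60 gives an upper limit of 4.9%, so x = 0 and x = 1 both miss: 4.6% + 14.6% = 19.2%.

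With 0/60 the interval is 0 to 0; the Wilson and Clopper-Pearson upper limits are both 6.0%. The chance of 0/60 is 0.99^60 = 55% at a true rate of 1% and 0.98^60 = 30% at 2%. Lower limits at 1, 2 and 3 of 60 are −1.6%, −1.2% and −0.5%.

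**The case against.** **The specific section should override the general one.** SAP 6.3.10 and 6.3.11 name a population, a method and a missing-data rule, and the SAP may modify the protocol, so a programmer would produce one result. This shows that a result would be produced, but it does not remove the conflict: the rule for secondary endpoints has no exception, and none is stated for the EMA.

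**The p-value example is favourable to the concern.** This stands. Among the cases tabulated, only 36 per arm with 15/5% missingness crosses 0.05. Exclusion of PHQ-8 scores of 15 or more and of current major psychiatric disorder may also make the depression subset smaller than assumed. The example shows that the choice can matter, not that it will.

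**The intervals are only descriptive.** Also true. Comparisons to Week 24 use MN with F and G pooled to about 120, no hypotheses are tested afterwards, and counts appear beside the interval. Coverage at n = 60 is acceptable from about 10% upward. The problem is confined to F and G while on placebo, early visits, and possibly 10 mg. Within that range the printed error bars are still wrong, and the plan expects those rates.

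**Conclusion.** Both parts hold. For the EMA and VHP authorities, the SAP assigns HADS improvement to Analysis 1 by its general rule and to observed cases by its specific sections, with nothing to reconcile them. For the overall study and FDA/PMDA, observed case is consistent with SAP 5.3. The numerical effect cannot be fixed from the documents; under the assumed inputs a 10-point difference becomes anything from 4.5 to 13.5 points.

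The interval finding depends only on the sequence size and the true rate. Nominal 95% coverage at n = 60 falls to 81% at a true rate of 5% and 45% at 1%. Everything here is descriptive or outside alpha control, so this is a correction that should be made rather than a threat to the trial's main conclusions.

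**What to change.** **HADS.** In SAP 6.3.10 and 6.3.11, state that for the EMA and VHP authorities improvement up to Week 24 is analysed by Analysis 1 (COVID-19 missing excluded, other missing counted as not improved), with observed cases as supportive. An explicit, justified exception would also remove the contradiction, but Analysis 1 is the rule the plan already sets. The cost is lower reported improvement rates, because non-COVID missing subjects count as failures.

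**Intervals.** In SAP 5.2.1.4, replace the normal approximation with Wilson or Clopper-Pearson. Clopper-Pearson is conservative (coverage 97.6-99.5% at true rates of 1-5%, n = 48-60). Wilson is tighter but can fall to about 90% at a true rate of 1% for n = 48-55.

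**Editorial.** SAP 6.2.3, 6.2.4, 6.2.5, 6.2.7 and 6.2.8 could repeat the statement in 6.2.6 and 6.2.10 that descriptive summaries use observed cases; 5.2.1.4 already governs.

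All of this is SAP wording and small changes to table code, with no effect on design, data collection or power.

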5.2.2. Exposure response analysis

A Bayesian three-parameter maximum effect attributable to the drug (E_{\max}) exposure-response model will be used as the primary analysis approach to characterize the dose-response relationship. The response function will be the log odds (logit) of the proportion of subjects with response based on SALT ≤ 20 at Week 24 (or SALT ≤ 10 at Week 24, as applicable). In modeling the exposure response, the effect of loading dose will be included as a fixed factor in the model. Model-based estimation of the treatment effect for each dose compared to placebo will be presented.

5.2.2.1. Logistic regression analysis for the evaluation of effect of loading dose

The evaluation of the effect of loading versus no loading dose on the response at Week 24 will be assessed by logistic regression applied to the data from the 30 mg and 50 mg maintenance doses, with and without the loading dose. Data from placebo and the 10 mg dose will not be included in this analysis. There will be a single indicator variable for loading (treatment during the first 24 weeks) versus no-loading dose, and a single indicator variable for the effect of the 30 mg versus 50 mg maintenance doses. If there is evidence of a loading dose effect, an E_{\max} model as specified in Model 1 will be used. In this case, an additional term for the effect of loading dose is added to the E_{\max} model.

Although an interaction effect large enough to produce a significant interaction would be surprising, a check for interaction will be conducted using a similar logistic regression model, which includes interaction terms between the loading and maintenance doses. If the interaction effect is significant, exploratory analyses and follow-up work will be needed, and E_{\max} modeling will not be performed. No models will be pre-specified for this condition.

5.2.2.2. E_{max} models for exposure response analysis

- a. If the loading dose is significant in the logistic regression model in [Section 5.2.2.1](#), then an indicator variable will be added representing the loading dose effect to the E_{max} model.

$$\log\left(\frac{\pi}{1-\pi}\right) = E_0 + \frac{E_{max} * Dose}{ED_{50} + Dose} + \beta I_{(loading)} \text{ (Model 1)}$$

- b. If the effect of loading dose is not significant in the logistic regression model in [Section 5.2.2.1](#), the data with/without loading doses will be pooled for each maintenance dose and analyzed using the E_{max} model.⁵

$$\log\left(\frac{\pi}{1-\pi}\right) = E_0 + \frac{E_{max} * Dose}{ED_{50} + Dose} \text{ (Model 2)}$$

In either case, the results on the logistic scale of the E_{max} model will be back-transformed to the probability scale to improve interpretability and the posterior distribution for the difference on the proportion of SALT responders between the treatment groups determined by each dose and placebo will also be displayed.

